#### 4.7 Partial/Missing Dates

Partial or missing dates in general will not be imputed (medical history, previous cancer treatment).

For the calculation of the time (in months) from initial diagnosis of primary site to first date of IMP and time since most recent recurrence/relapse or progression to start date of IMP, the following imputation rules will be applied when the date of first diagnosis or date of most recent recurrence/relapse or progression is incomplete:

- If the day is missing: first day of the month
- If the day and month are missing: first day of July.
- If the day and month are missing and if the year is the same as the start year of IMP: leave missing.

For the assignment to prior or concomitant medication the following rules will be applied in case of incomplete or missing dates:

- If medication is ongoing or end date is missing, then medication will be considered as concomitant and missing date(s) will not be imputed.
- If end date is incomplete: if the day is missing: the end date will be imputed with the last day of the month; if the day and month are missing: the end date will be imputed with min (31 December of the year, last contact date, date of death).

The imputed dates will only be used for the assignment to prior or concomitant medication and will not be used in any other calculation and will not be listed.

For new anti-cancer therapy, when the start date is partial or missing, the date will be imputed:

- if start date is missing, but end date is not missing: the start date will be set to the end date.
- if start date remains missing, the start date will be set to the minimum of (last contact date and date of death).
- if start date is incomplete: if the day is missing: the start date will be imputed with the last day of the month; if the day and month are missing: the start date will be imputed with min (31 December of the year, the last contact date, date of death, end date if not missing).

The imputed dates will only be used to define the start of the new anti-cancer therapy for progression free survival and will not be used in any other calculation and will not be listed.

Page 13 of 44

TPL N°: eTPL SA-02-01

TPL Version: 02

Of SOP SA-02.08 TPL Effective Date: 31 Mar 2016

For the assignment of adverse events (AE) the following rules will be applied in case of incomplete or missing start date:

• if end date is before the date of first IMP administration, the start date will remain missing (medical history);

Version: 2.0

- If start date is missing and end date is after or on the date of first IMP administration or the end date is missing, the start date will be imputed by the date of first IMP administration (AE).
- If start date is incomplete and end date is after or on the date of first IMP administration or the end date is missing, the start date will be imputed as follow:
  - if the day is missing and if the start date and date of first dose share the same month and year, the missing start day will be imputed as the day of first dose. If the start date month is after the month of first dose, day will be imputed as the first (i.e. 01-MMM-YY);
  - if the day and month are missing and if the start date and date of first dose share the same year, day and month will be imputed as the day and month of first dose. If the start date year is after the year of first dose, the month and day will be imputed as January first (i.e. 01-JAN-YY).

The imputed date will only be used for the assignment of the treatment-emergent flag to adverse events and will not be used in any other calculation (unless specified otherwise) and will not be listed (i.e. only date as recorded will be listed).

#### 4.8 Methods to Be Used for Handling Missing Data

All available data will be included in data listings and tabulations. Imputed dates will not be included in the listings.

No imputation of missing data is planned for safety endpoints, PK or biomarker endpoints. If outliers are detected, a robustness analysis where the outlier effect is reduced or eliminated may be considered.

Any subjects with missing information regarding response to treatment will be counted as non-responders. This also includes subjects with response that cannot be confirmed according to RECIST  $v1.1^2$  criteria.

For PK data, missing concentration values will be reported as is in data listings. Concentration values below the lower limit of quantification will be handled as LLOQ/2 in summary statistics and reported as is in data listings. Any missing concentration data will not be imputed.

## 5. Changes to Protocol

The definition of the DDS differs from the protocol v9.0: The DDS includes subjects with a dose reduction (below 80% of the planned dose) due to abnormal ALT/AST measurements, those are evaluable for MTD and included in the DDS.

The PK analysis set was not specified in the protocol v9.0. PK analysis set needs to be defined as PK is essential to correctly select the RP2D and can only be evaluated based on the dosed subjects.

Page 14 of 44

Of SOP SA-02.08 TPL Effective Date: 31 Mar 2016

TPL N°: eTPL SA-02-01

The protocol (section 4.1) opened for the possibility to further explore dose regimens in an expansion part. This possibility is not used.

## 6. Trial Subjects

## **6.1 Subject Disposition**

Screening failures including failure reason, protocol version and re-screening information will be presented in a listing. Subjects who were screened but never started trial treatment will be included in the same listing. The number of screen failure and the screen failure reasons will be tabulated. Reason for not receiving the treatment will be listed.

The number of subjects in each analysis set will be tabulated as defined in section 4 and overall.

The frequency of subjects treated, of subjects who discontinued the trial treatment ('end of treatment') and of subjects who terminated the trial ('end of trial') will be given for the full analysis set (FAS). A subject will be considered as having completed the trial when all planned trial visits have been performed, including end-of-treatment visit and safety FU visit. The primary reason for discontinuation of treatment and the primary reason for withdrawal from the trial will both be summarized. The details of the 'other reason' will be included in the listing together with other discontinuation details.

A listing of all subjects screened including site, country, ICF date and version, screening number, ICF form date, and population flags will be presented.

Subject dispositions and reasons for discontinuation (of treatment or the trial) will also be presented in a flow diagram in accordance with the current CONSORT statement.

#### **6.2 Important Protocol Deviations**

The important major protocol deviations will be summarized by dose-level and overall for all subjects. The details of all deviations will be listed.

In addition, Covid-19 related PDs will be listed separately:

- All important PDs related to Covid-19;
- All non important PDs related to Covid-19 (major, minor);
- Subject listing of missed/changed visits;
- Subject listing of efficacy assessments missed due to visits impacted by Covid-19.

A summary table of the above might be added to evaluate the impact of Covid-19.

Protocol violations will be defined in the protocol deviations plan.

#### 6.3 Inclusion and Exclusion Criteria

Listing of all inclusion and exclusion criteria not met will be listed.

Information on informed consent will be presented in the disposition listing.

F

Page 15 of 44

TPL N°: eTPL SA-02-01 Of SOP SA-02.08 TPL Effective Date: 31 Mar 2016

## 7. Demographic Characteristics

Descriptive statistics with respect to subject characteristics at baseline will be displayed for the FAS. Those outputs may be displayed for the DDS set and PK set if those population sets differ from more than 20% compared to the FAS.

The variables to be summarized are:

- Gender (Male/Female)
- Age (years, continuous and categorical: age < 65 years and age ≥ 65 years)
- Race (White, Black or African American, Native Hawaiian or other Pacific Islander, Asian, American Indian or Alaska native, Other)
- Country (Spain, United Kingdom, United States)
- Ethnic origins (Hispanic or Latino, Not Hispanic or Latino)
- Weight (kg) at baseline
- Height (cm)
- BMI (kg/m²) at baseline
- Contraception data, only for female subjects:
  - Subject considered as sterilized or infertile (Yes, No)
  - Reason (Surgical sterilization, Postmenopausal, Other)
  - Subject practice adequate contraception (Yes, No)
  - Type of contraception (pills/implant/vaginal device/injections/transdermal patches/other)

Smoking and drinking history will be presented in listings as individual data. Details of the 'other' categories mentioned above will be added to the listings.

## 8. Baseline Disease Characteristics

Descriptive statistics with respect to subject disease characteristics at baseline will be displayed for the FAS.

- Type of cancer at time of diagnosis (Advanced and/or metastatic CRC, NSCLC, TNBC, RCC, Gastric (incl. esophagogastric junction) cancer, Pancreatic cancer, Urothelial cancer)
- ECOG performance status (0-5). Note: at entry only subjects with an ECOG performance status of 0 and 1 are allowed.
- Tumor stage at screening (I, IA, IB, II, IIA, IIB, III, IIIA, IIIB, IV, IVA, IVB, IVC) by indication.
- Histological results (see CRF for the details) by indication
- Histological subtype (see CRF for the details) by indication
- Histological grade (GX, G1, G2, G3, G4)
- Mutational status (e.g.: EGFR mut, ALK rearrangement, BRAF, NRAS, None) and mutational sub-term (T790M, L858R, ...) combined
- Receptor status (ER+, ER-, PR+, PR-, HER2+, HER2-, Other, None)

TPL Version: 02

• Time (in months) from initial diagnosis to start date of IMP

Page 16 of 44

TPL N°: eTPL SA-02-01 Of SOP SA-02.08 TPL Effective Date: 31 Mar 2016

 Time (in months) since most recent recurrence/relapse or progression to start date of IMP

Version: 2.0

Tumor stage at time of diagnosis (I, IA, IB, II, IIA, IIB, III, IIIA, IIIB, IV, IVA, IVB, IVC), reason tumor staging not performed, tumor classification (TNM), target and non-target lesions details at time of diagnosis, and details of the other categories mentioned above will be added to the listings.

## 9. Biopsy

Descriptive statistics with respect to the biopsy information at baseline will be displayed for the FAS.

The variables to be summarized are:

- Biopsy performed (Yes, No) at screening\*
- Type of biopsy (Fresh, Archived, both) available at screening\*
- Time since last biopsy before first date of IMP (months)

Reason biopsy not done will be added to the listings. Time since biopsy to start date of IMP (months) will be added in the listing for each biopsy performed Reason for biopsy failure will be listed only (free text).

## 10. Medical Procedures and Surgical History

Medical conditions and Surgeries will be coded using the Medical Dictionary for Regulatory Activities (MedDRAc).

The medical conditions will be tabulated separately for active (ongoing at screening) and non-active conditions by system organ class (SOC) and preferred term (PT) for the FAS. Surgeries will be tabulated separately in the same way. SOC will be ordered by decreasing frequency and PT (within SOC) will be ordered by decreasing frequency in total. As mentioned in the section 17.3 of Adverse Events, the adverse events collected during the pre-treatment period will be tabulated together with the medical history.

All details will be listed.

## 11. Prior Anti-Cancer Therapies

Prior systemic anti-cancer therapies will be summarized for the FAS as described below.

Prior systemic therapies in the metastatic setting will be listed and tabulated by first and fourth Anatomical Therapeutic Chemical class (WHO-DD dictionary, ATC 1 name and ATC 4 name) for the FAS. ATC classes will be ordered by decreasing frequency.

Prior radiation therapies and anti-cancer surgeries will be coded using the Medical Dictionary for Regulatory Activities (MedDRA) and presented separately by system organ class and preferred term (both ordered by decreasing frequency in total).

Page 17 of 44

TPL N°: eTPL SA-02-01 Of SOP SA-02.08 TPL Effective Date: 31 Mar 2016

\* independent if at screening or re-screening visit.

<sup>c Most recent MedDRA version at the time of production

In addition, the number of prior systemic treatment lines will be summarized by means of descriptive statistics and by category (1, 2 and  $\geq$ 3). Regimen consisting only of radiotherapy or surgery will not be counted as systemic treatment, but a regimen with systemic therapy and surgery/radiotherapy will be counted as systemic.

Version: 2.0

The number of subjects by combination of drugs as 1st line systemic regimen (first combination received), and the number of subjects by combination of drugs as 2nd line systemic regimen (second combination received) will be presented by indication.

The best response to the latest prior cancer therapy and to the second last prior cancer therapy will be tabulated.

In addition to the tabulation by dose a similar tabulation by tumor type (indication) will be presented.

All details will be listed.

## 12. Subsequent Anti-Cancer Therapies

Subsequent cancer therapies will be summarized for the FAS as described below.

Subsequent systemic cancer therapies will be listed and tabulated by first and fourth Anatomical Therapeutic Chemical class (WHO-DD dictionary, ATC 1 name and ATC 4 name) for the FAS. ATC classes will be ordered by decreasing frequency.

On-study radiation therapy and surgeries will be coded using the Medical Dictionary for Regulatory Activities (MedDRA) and presented by system organ class and preferred term. SOC and PT (within SOC) will be ordered by decreasing frequency in total.

In addition to the tabulation by dose, a similar tabulation by tumor type (indication) will be presented.

All details will be listed.

#### 13. Procedures

Procedures will be coded using the Medical Dictionary for Regulatory Activities (MedDRA).

The medical procedures will be tabulated by system organ class (SOC) and preferred term (PT) for the FAS. Table will be ordered by decreasing frequency of SOC and by decreasing frequency of PT within SOC in total. All procedures will be listed.

#### 14. Prior and Concomitant Medication

Prior and Concomitant medications will be classified according to WHO-DD dictionary.

Medications will be reported according to the following two distinct categories:

- Prior when they start and end before the first day of trial treatment.
- Concomitant when they start before the first day of trial treatment and stop or continue after the first day of trial treatment, or when they start on or after first day of trial treatment. Concomitant medication should start or continue during the on treatment period.

The number and percentage of subjects receiving a concomitant medication will be displayed by first and fourth Anatomical Therapeutic Chemical class (WHO-DD dictionary, ATC 1 name and ATC 4 name) for the FAS. ATC classes will be ordered by decreasing frequency.

Page 18 of 44

TPL N°: eTPL SA-02-01 Of SOP SA-02.08 TPL Effective Date: 31 Mar 2016

Approved in Vault: 07 Mar 2022

A listing of all medications recorded on the (prior and) concomitant medications CRF page will provide details including indication, dose, route, frequency, and start and stop dates. Prior and Concomitant medications will be listed separately. Also, the specific AE or medical history event will be included where applicable.

Version: 2.0

## 15. Efficacy Evaluation

Efficacy results will be presented on the full analysis set (FAS).

The RECIST v1.1 guidance will be used to derive the response and progression endpoints. A confirmation is not required as such per protocol, but both categories of endpoints (confirmed and un-confirmed) will be derived.

#### 15.1 Dose Escalation Part

The evaluations described in this section are part of the secondary objectives. The primary objective is described in the Safety Evaluation section 17.

## 15.2 Tumor Shrinkage

Anti-tumor activity measured by tumor shrinkage (based on sum of the diameter(s) of all target lesions from the CT-scan evaluations) will be listed and summarized graphically by:

- Individual plots (waterfall and spider plots)
- waterfall plots of the maximal response (maximal reduction in the sum of diameters in the target lesions) at any time on trial

Summaries will be presented as described in section 4 per assessment. The largest tumor shrinkage and its change from baseline will also be presented. Missing values are imputed using the method specified in section 4.8 (Table 3 in Eisenhauer EA, Therasse P, Bogaerts J, et al. New response evaluation criteria in solid tumours: revised RECIST guideline (version 1.1). European journal of cancer (Oxford, England: 1990). 2009;45(2):228-247. Eisenhauer et al., 2009).

#### 15.3 Best overall response (BOR)

The time point (per visit) response categories per RECIST v1.1 guidance are: complete response (CR), partial response (PR), stable disease (SD), progressive disease (PD), and not evaluable (NE).

The best overall response is the best response across all time points, where Table 3 in Eisenhauer EA, Therasse P, Bogaerts J, et al. New response evaluation criteria in solid tumours: revised RECIST guideline (version 1.1). European journal of cancer (Oxford, England: 1990). 2009;45(2):228-247. Eisenhauer et al. (2009) describes how a response is to be confirmed when possible.

Confirmed objective response rate (ORR) is defined as an overall response (PR or better) confirmed by a subsequent overall response of PR or better at least four weeks later\*. Of note, the best overall response is the best response recorded from the start of the treatment until disease progression/recurrence or start of new anti-cancer therapy.

The date of the confirmed response is the date of first occurrence of response.

[\* The following sequences will be counted as confirmed response:

CR-CR = CR confirmed

TPL N°: eTPL SA-02-01 TPL Version: 02

Of SOP SA-02.08
TPL Effective Date: 31 Mar 2016
Approved in Vault: 07 Mar 2022

- CR-PR = PD (confirmed) because of reappearance of disease. with sas checks, we
  must make sure that prior scan is corrected to PR if believed when seeing the
  following scan to be only PR at subsequent scan. This way CR-PR should not occur
  if the reader interprets this as a PR confirmed, it would be corrected to PR-PR in
  this case. Otherwise, it would be CR-PD which would qualify as confirmed SD if
  minimum duration criteria for SD met.
- PR-PR = PR confirmed
- PR-CR = PR confirmed

NB: two intermediate missing (NE) scan evaluations between the response scan and the confirmation scan are allowed, e.g. the sequences PR-NE-PR and PR-NE-NE-PR will be considered PR confirmed.

In all cases the scan that confirms the first scan with CR/PR must occur no sooner than 4 weeks after the first scan.

A subject with sequences that qualify both as PR confirmed and CR confirmed, e.g. PR-PR-CR-CR would be considered a CR confirmed.

If PR or CR are not confirmed, the response will be SD when on or after 35 days after first IMP and NE when before 35 days. (The 35 days takes into account the minimal 6-weeks duration +/-1 week window before first post baseline scan.)

Best overall response will be summarized descriptively. Subjects with no post-baseline data will be identified by NE for best response.

The best overall response is presented with exact 95% confidence interval using the Clopper-Pearson method.

As a supportive analysis, the best response including both confirmed and unconfirmed responses is presented similarly. (The unconfirmed response does not require a confirmatory scan for e.g. CR or PR.)

CR and PR should be confirmed for the final analysis. If any data should be published before the final database lock (i.e Interim analysis), CR pending confirmation and PR pending confirmation categories will be used.

## 15.4 Objective response rate (ORR)

The objective response rate is the proportion of subjects with either CR or PR as best overall response. This is presented as part of the BOR summaries.

Similarly, the ORR including both confirmed and unconfirmed responses will be presented as a supportive analysis.

In addition, ORR will be analyzed by subgroup (as described in section 4.4) using a forest plot.

## 15.5 Time to response (TTR)

Time to response (TTR) will be calculated on subjects responding. It is defined as the number of days from Day 1 in Cycle 1 to the first documented response of either CR or PR, which can be subsequently confirmed (although date of initial response is used, not date of confirmation).

Page 20 of 44

TPL N°: eTPL SA-02-01 Of SOP SA-02.08 TPL Effective Date: 31 Mar 2016

TTR will be listed and summarized using descriptive statistics. Results will be graphically displayed as a Kaplan-Meier curve, starting from 0% (no responder) to 100% (all responders).

## 15.6 Progression free survival (PFS)

PFS is defined as the time from the date of C1D1 to the date of the first documented progression or death due to any cause. PFS will be assessed via local review according to RECIST  $1.1^2$ .

PFS will be censored in accordance with Table A in Appendix 3 in the FDA Guidance for Industry "Clinical Trial Endpoints for the Approval of Cancer Drugs and Biologics (2007)". In summary, PFS will be censored if no event (progression or death) is observed before the first of (i) the analysis cut-off date, and (ii) the date when a new anti-cancer therapy is started. The censoring date will be the date of the last adequate tumor assessment prior to cut-off/start of new anti-cancer therapy.

Subjects continuing without disease progression or death will be censored and the censoring date will be the date of the last adequate tumor assessment prior to data cut-off/start of new anti-cancer therapy. If there are no post-baseline scans available, then it will be censored at the date of the first IMP.

In case an event occurs after more than 2 missed scans, the censoring is done at last adequate assessment date before the missed scans. The definition of '2 missed scans' is equals to 98 days, the equivalent of 2 \* (6 weeks + 1 week of windowing).

If last scan date before the PD or death date is less or equal to 350 days (50 weeks) after start of IMP and the PD or death date is greater than 98 days (6+1 weeks \*2) after this last scan date, then it will be censored at last scan date.

If last scan date before PD or death date is greater than 350 days (50 weeks) and less or equal to 441 days (50+13 weeks) after start of IMP and the PD or death date is greater than 140 days (50+13 weeks) after this last scan date, then it will be censored at last scan date.

If last scan date before the PD or death date is greater than 441 days (7+13 weeks) after the start of IMP and PD or death date is greater than 182 (12+1 week \*2) days after this last scan date, then it will be censored at last scan date.

Progression-free survival will be derived and listed for all subjects as well as summarized using survival analysis methods:

- Kaplan-Meier curves
- Kaplan-Meier estimate of the median time, the first and third quartiles, along with approximate 95% confidence interval of the median (the default conftype=loglog in SAS PROC LIFETEST will be used).

The number of events may be small, and thereby limit use of the Kaplan Meier method to provide reliable information. In this case, descriptive statistics (e.g., n, mean, standard deviation, median, minimum, and maximum) for PFS will be presented.

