⁶ During the trial, body weight is measured on the dosing day, as part of the dose calculation. Please see section 9.4.1.
⁷ Temperature, blood pressure and heart rate. Please see Table 1-5 and section 9.4.2.
⁸ Mandatory PET-CT scans must be taken at screening and, if avid at screening, also at Cycle 2 Day 2, and week 12 (±7 days). Please see section 9.2.
⁹ A CT scan must be performed at Cycle 3, Day 8-14 after first dose. If PET-CT at screening showed no avidity, a CT scan has to be done instead of a PET-CT in week 12 (±7 days). From week 18 (±7 days)
until week 50 after first dosing. CT scans must be performed every 6 weeks (±7 days), and every 12 weeks (±7 days) thereafter until disease progression is assessed by the investigator, the start of new anti-
cancer therapy, withdrawal of consent, or death, whichever occurs first. Imaging assessments should follow calendar days and should not be adjusted for delays in cycle starts.
¹⁰ All laboratory parameters will be analyzed centrally, except urinalysis. In the first 3 cycles, all biochemistry safety parameters must be assessed locally as well to monitor liver function. At treatment visits,
laboratory parameters will also be analyzed at local laboratory prior to treatment of IMP please see section 9.5.
¹¹ Serum (beta-hCG) laboratory test should be taken at screening. A urine pregnancy test should be taken before every treatment of IMP.
¹² HbsAg, anti-HBs and anti-HBc, Hepatitis C and antibodies to CMV antigen will be assessed at screening for all patients. At end of treatment, only antibodies to CMV antigen will be assessed. Please see
section 9.5 for further details.
¹³ The latest archived biopsy can be used preferably derived from advanced disease stage. If no sample is available, a new tumor biopsy must be obtained.
¹⁴ Optional.
¹⁵ All patients must have a sample taken at Day 1 and 8 of Cycle 1 and at Day 8 of Cycle 3. If the visit occurs on an infusion day, the sample must be taken before IMP treatment.
¹⁶ Sample to be taken at Cycle 3.
¹⁷ Sample to be taken at Cycle 6.
¹⁸ Only non-serious AEs \geq 3 possibly related to IMP and SAEs (independent of causality).
¹⁹ Only new anticancer treatments.
²⁰ Patient status at withdrawal.
²¹ If the patient withdraws sooner than 70 days after the last dosing, the safety follow-up visit should take place at the time of withdrawal unless there has been a safety follow-up visit within the last 14 days.

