9.2.1 Dose Escalation Part

In the dose escalation part, PET-CT scans must be taken at screening and, if avid at screening, also at Cycle 2 Day 2, and week 12 (\pm 7 days). If a patient, who has been exposed to GEN1029, did not have any PET-CT scans while on treatment and the PET-CT scan at screening displayed avidity, a PET-CT scan should be taken at the end of trial visit (please refer to Section 9.2.3 for additional details on PET-CT scans).

The PET-CT scan at screening is with contrast of thorax, abdomen and pelvis. If there is suspicion of brain metastases or tumors, a scan of the head will be performed before inclusion.

Up to five target lesions (maximum two per organ) will be defined at screening and these must be followed throughout the trial. Non-target lesions will also be assessed throughout the trial.

A CT scan must be performed at Cycle 3, Day 8-14 after first dose. If PET-CT at screening showed no avidity, a CT scan has to be done instead of a PET-CT scan in week 12 (\pm 7 days). From week 18 (\pm 7 days) until week 50 after first dosing, CT scans must be performed every 6 weeks (\pm 7 days), and every 12 weeks (\pm 7 days) thereafter. Imaging assessments should follow calendar days and should not be adjusted for delays in cycle starts.

Additional CT-scans may be performed at the investigators discretion to confirm response or new symptoms. The intervals should not be shorter than four weeks. In this case the investigator must choose the imaging technology based on the clinical indication. Information from additional scans should be added to an unscheduled visit in the eCRF

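### The missed-scan limits in SAP 15.6 do not match the scan intervals around week 50, so a progression found after one missed scan is censored there and counted elsewhere

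*SAP*

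**What the plan says.** **Scan calendar.** Protocol 9.2.1 and footnote 9 to Table 1-1 require a CT in Cycle 3 between Days 8 and 14 (about week 6) and a scan at week 12. A 6-weekly phase starting at week 18 is set out in 9.2.1: "until week 50 after first dosing, CT scans must be performed every 6 weeks". The 12-weekly phase is described in the footnote as follows: "and every 12 weeks (±7 days) thereafter until disease progression is assessed by the investigator". Both phases carry a window of one week either way. Dates follow the calendar and do not move with delayed cycles. Neither place says from which week the 12-weekly series is counted. Extra scans are possible, not less than four weeks apart: "Additional CT-scans may be performed at the investigators discretion to confirm response or new symptoms".

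**Censoring rule.** SAP 15.6 states a principle: "In case an event occurs after more than 2 missed scans, the censoring is done at last adequate assessment date before the missed scans". It equates two missed scans with 98 days and then gives three limits, each chosen by the date of the last scan:

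- Last scan "less or equal to 350 days (50 weeks) after start of IMP and the PD or death date is greater than 98 days" after it: censored at that scan.
- Last scan "greater than 350 days (50 weeks) and less or equal to 441 days (50+13 weeks) after start of IMP" and event "greater than 140 days (50+13 weeks) after this last scan date": censored at that scan.
- Last scan "greater than 441 days (7+13 weeks) after the start of IMP" and event more than 182 days after it: censored at that scan.

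SAP 15.7 applies FDA-based censoring to DoR but refers the reader to 15.3, which deals with best overall response.

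**The concern.** Each limit is the length of two consecutive scan intervals plus windows. Such a limit works only if those are the two intervals that follow the last scan. Around the change from 6-weekly to 12-weekly scanning they are not. The last 6-weekly scans keep the 6+6-week limit although they run into 12-week gaps. The first 12-weekly scan gets the 6+12-week limit although two 12-week gaps follow.

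The same attendance pattern is therefore an event or a censored time depending only on when the last scan fell. The censoring is triggered by the event itself, so it is informative: a progression is removed and replaced by a censored time months earlier. This tends to make the Kaplan-Meier tail too high. SAP section 4 also asks for 12- and 24-month event-free rates.

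**Working it through.** **1. The SAP's own figures.**

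- 2 × (6+1) × 7 = 98 days
- (6+1+12+1) × 7 = 140 days
- 2 × (12+1) × 7 = 182 days
- Cut points: 50 × 7 = 350 and (50+13) × 7 = 441

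The day counts reproduce. The bracketed week labels on 140 days (should be 7+13) and 441 days (should be 50+13) are swapped.

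**2. One missed scan, progression at the next scheduled scan.** Scheduled scans are at weeks 6, 12, 18, 24, 30, 36, 42 and 48, then 60, 72, 84 and so on. The gap is the nominal difference in days; the range lets both scans move ±7 days.

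| Last scan | Missed | PD found at | Gap (range) | SAP limit | Result |
|---|---|---|---|---|---|
| weeks 6–36 | next | second next | 84 (70–98) | 98 | counted |
| week 42 (day 294) | 48 | 60 (day 420) | 126 (112–140) | 98 | censored |
| week 48 (day 336) | 60 | 72 (day 504) | 168 (154–182) | 98 | censored |
| week 60 (day 420) | 72 | 84 (day 588) | 168 (154–182) | 140 | censored |
| week 72 on | next | second next | 168 (154–182) | 182 | counted |

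In every row the whole range lies on one side of the limit, so attendance within the windows cannot change the result. The progressions lost are replaced by censoring 18, 24 and 24 weeks earlier.

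**3. Other anchors for the 12-weekly scans.**

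- Weeks 62/74/86: week 42 to 62, 140 (126–154) > 98; week 48 to 74, 182 (168–196) > 98; week 62 to 86, 168 (154–182) > 140. Censored after weeks 42, 48 and 62.
- Weeks 54/66/78 (needs a 6-weekly scan after week 50): week 48 to 66, 126 (112–140) > 98; week 54 to 78, 168 (154–182) > 140. Censored after weeks 48 and 54.

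All other on-trial scheduled scans give a counted event.

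**4. Deaths and unscheduled progressions after one missed scan (60/72/84, nominal dates).** The period with exactly one scheduled scan missed lasts 84 days in each case. The part lost is the gap to the second next scan minus the SAP limit.

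- After week 42: 126 − 98 = 28 days (days 99–126 after the scan)
- After week 48: 168 − 98 = 70 days (days 99–168)
- After week 60: 168 − 140 = 28 days (days 141–168)

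**5. Two missed scans, progression at the next scheduled scan (60/72/84).** Gaps are 126 days after weeks 6–30, 168 after week 36, 210 after week 42 and 252 after week 48, all > 98; 252 > 140 after week 60; and 252 (238–266) > 182 from week 72. All are censored, although the stated principle requires more than two.

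**The case against.** **A reader might infer that every event after one missed scan near week 50 is lost.** The documents do not support that. By step 4, of the 84 days with exactly one scan missed, 56, 14 and 56 still count for deaths and unscheduled progressions after weeks 42, 48 and 60. The finding is exact only for progression at the next scheduled scan after an on-trial scheduled scan. Unscheduled last scans behave differently. With a last scan on day 322, week 48 missed and progression at week 60, the gap is 420 − 322 = 98 on the nominal date (counted) but 105 if that scan is 7 days late (censored). The SAP also does not say whether the screening scan can serve as the last scan.

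**A reader might also infer that an event can be censored with no scan missed.** This needs a first 12-weekly scan at week 62. The gap from week 48 is then 98 days (84–112), above 98 in 105 of 225 window combinations (47% if all are equally likely). The SAP's 441 = 350 + 91 hints at that calendar, but the protocol does not state it, and it implies a 14-week interval where the protocol names only 6 and 12 weeks. It remains conditional.

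**In defence of the 98 days,** the SAP defines two missed scans by that number, so more than two could be read as more than 98 days. That makes the 6-weekly limit workable as a rule for two or more missed scans. It does not reconcile it with a literal count, and it does not help around week 50.

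**On importance,** PFS is a secondary endpoint without a test, the expansion part was not started, and no reported estimate is shown to change. That stands and limits the weight of the point. It does not make the rule correct.

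**Conclusion.** The rule is wrong as written and should be corrected; the effect is probably small. The fault appears on all three calendars compatible with the text and does not depend on attendance within the windows. It rests on reading the limits literally and on scheduled scans.

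If two or more missed scans are meant, only subjects progression-free to about week 42 are exposed. For scheduled last scans the earliest event that can be lost is on day 287 + 99 = 386. The 12-month rate then changes only through a smaller risk set, while the later curve and the 24-month rate can lose the event itself. The documents do not say how many of the 48 subjects reach that point, so a material distortion of PFS cannot be claimed.

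If more than two is meant literally, the 98-day limit is too short from the first scans on: with a last scan on day 42 and weeks 12 and 18 missed, an event on day 141 is already censored.

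**What to change.** 1. State the week from which the 12-weekly scans are counted, and whether censoring starts at two missed scans or only after more than two.
2. Replace the day bands with a rule computed for each subject from the protocol calendar: censor at the last adequate scan if the event falls later than the second next scheduled scan plus 14 days (third next if more than two is meant). Count from the recorded visit for a scheduled scan and from the actual date for an unscheduled one.
3. For scheduled last scans on 60/72/84 with two or more, this gives 84 + 14 = 98 days through week 36, 126 + 14 = 140 at week 42 and 168 + 14 = 182 from week 48. By steps 2 and 5, one missed scan is then always counted and two always censored.
4. Do not turn these values into new fixed bands. For an unscheduled last scan on day 322 the rule gives 420 − 322 + 14 = 112 days. A 182-day band would count a progression on day 504 (gap 182) after two missed scans.
5. Point SAP 15.7 to 15.6 so that DoR follows the same rule, and correct the labels on 140 days (7+13 weeks) and 441 days (50+13 weeks).

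The cost is one clarification of the calendar, a change to the PFS and DoR program and a few lines of SAP text. No new data are needed.
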